2 SAMPLE SIZE DETERMINATION

The determination of the number of participants is based on clinical rather than statistical considerations. Taking into consideration the guideline from Committee for Medicinal Products for Human Use (EMEA/CHMP/BPWP/144533/2009 rev.2), approximately 65 PTPs will be enrolled to obtain at least 50 participants with at least 50 EDs at the end of the study. All eligible participants completing or remaining at the end of study will be offered participation in the planned extension trial.

At least 12 participants in each age cohort need to have completed adequate blood sample collection to assess key PK parameters.

3 ANALYSIS POPULATIONS

The following populations for analyses are defined:

Population	Description			
All-Enrolled Analysis Set	All participants who were enrolled in the study, regardless of whether they were dosed with study drug or not.			
	Participants will be considered enrolled when the Investigator has verified that they are eligible according to the criteria in Section 5 of the protocol. Participant disposition and enrollment summaries will be based on the All-Enrolled Analysis Set.			
Full Analysis Set	All participants who take at least 1 dose of study intervention.			
	All analyses of demographics, baseline characteristics, and efficacy will be based on the FAS, unless otherwise specified.			
Safety Analysis Set	The safety analysis is the same as the Full Analysis Set and will include all participants who receive at least one dose of study drug.			
	All analyses of safety will be based on the Safety Analysis Set, unless otherwise specified.			
Per Protocol Set	A subset of the Full Analysis Set including participants who do not have important protocol deviations potentially impacting efficacy.			
	The Per Protocol Set will be utilized for sensitivity analysis of the efficacy endpoint of annualized bleeding rate.			
PK Analysis Set (PKAS)	All participants who have completed adequate blood sample collection to assess key PK parameters, as determined by the PK scientist.			
Surgery Subgroup	All participants who have undergone major surgery after the first dose of study drug.			

Table 3 - Populations for analyses

4 STATISTICAL ANALYSES

All summaries and statistical analyses will be generated using SAS Version 9.0 or higher.

4.1 GENERAL CONSIDERATIONS

Unless otherwise specified, all data will be summarized for each age cohort (<6 years and 6 to <12 years) and overall.

The surgery subgroup will be included in baseline tables as well as the overall AE summary. When the surgery subgroup is included in a summary table, participants who participated in the surgery subgroup will be included in the columns for age cohort and the surgery subgroup but will only be counted once in the overall column.

Baseline

Baseline is defined as the last non-missing measurement taken prior to the first dose of study drug, excluding measurements taken during a surgical/rehabilitation period. For HJHS, if there are no measurements taken prior to the first dose of the drug, and the first measurement is taken no more than 7 days after the first dosing, then this first measurement will be considered as baseline for HJHS.

Study Day

Study day is defined as the number of days relative to the date of the first dose of study drug. The first dose of study drug is Day 1. Study day will be calculated as (date of event – first dose date +1) if the date of event is on or after the first dose date or (date of event – first dose date) if the date of event is before the first dose date. If the date of event is missing or partial, the corresponding study day will be left blank.

Exposure Day

One exposure day (ED) is defined as a 24-hour period in which a participant receives 1 or more doses of study drug, with the time of the first injection of study drug defined as start of the ED.

4.1.1 Definition of study periods

This section defines the study periods used for different analyses, including treatment period, efficacy period, surgical/rehabilitation period, and safety period.

All analyses and summaries relating to bleeding and consumption will be based on the *efficacy period* (Section 4.1.1.2); data collected during the PK and surgical/rehabilitation periods (major and minor) will not be included.

All other efficacy analyses will be based on the *treatment period* (Section 4.1.1.1), excluding data that occurs during any major surgical/rehabilitation period to avoid confounding the treatment effect. Analysis of efficacy endpoints that are visit-based will not include visits that are coincidental with a major surgical/rehabilitation period.

Surgical evaluations will be based on the *surgical/rehabilitation period* (Section 4.1.1.3).

All safety analyses will be based on the *safety period* (Section 4.1.1.4). Unless otherwise specified, adverse events and laboratory evaluations occurred during major surgical/rehabilitation periods will not be included in the safety summaries.

4.1.1.1 Treatment period

The treatment period is defined as the actual treatment that the participant follows.

The start date and time of the treatment period is defined as the date and time of the first dose of study drug (or, if the time is not available, at 00:01 on the day of the first dose). The end date and time of the treatment period is defined as 23:59 on the day of the last dose of study drug.

The duration of treatment period is the time period from the start of the treatment period to the end of that treatment period. The total duration will be calculated in minutes and converted to days as the number of minutes divided by 1440.

4.1.1.2 Efficacy period

The efficacy period will be used for the evaluation of bleeding and consumption endpoints. For a participant to have an evaluable efficacy period over the duration of study, he/she must have at least 2 prophylactic dose of study drugs. The efficacy period is defined as the treatment period interrupted for PK periods, surgical/rehabilitation periods (major and minor) and large injection intervals as described below.

Adjustments Due to PK sampling period(s)

For participants undergoing PK sampling after their first dose of BIVV001, the efficacy period starts with the date and time of the first prophylactic dose following the completed PK sampling period (168 hours), and ends with the end of the treatment period as defined in Section 4.1.1.1. That is, if the initial PK sampling period is incomplete due to an aborted collection of blood samples following the PK injection (eg, because of a bleeding episode that required treatment), then the efficacy period will begin following a subsequent fully executed PK sampling period.

Adjustments Due to Surgical/Rehabilitation Periods

For analysis purposes, the efficacy period will be adjusted for all surgical/rehabilitation periods (major and minor). The start and end of the efficacy period are adjusted as follows:

- For all participants, the efficacy period continues up to 1 minute before the start of a surgical/rehabilitation period.
- For participants on a prophylactic regimen following the end of a surgical/rehabilitation period, the efficacy period for the prophylactic regimen re-starts at the first prophylactic dose following the end of the surgical/rehabilitation period.

Statistical Analysis Plan BIVV001-EFC16295 23-Aug-2021 Version number: 1

Bleeding episodes that occur during the surgical/rehabilitation period will be attributed to the surgical/rehabilitation period and hence not counted towards the ABR.

Adjustments Due to Large Injection Intervals

For analysis purposes, the efficacy period will also be adjusted to account for large intervals between injections resulting from missing data. A large interval is defined as >28 days between any 2 adjacent BIVV001 injections within a prophylactic treatment regimen, and any such intervals will be removed from the efficacy period. The efficacy period prior to each such interval will end at the time of the last injection prior to the interval and restart at the time of the next prophylaxis injection. The efficacy period will be adjusted for each identified interval that is not within a surgical/rehabilitation period.

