10.7.3 Hemophilia joint health score (HJHS)

10.7.4 Washout and blood sampling summary

The following tables summarize the requirements for washout and blood sampling necessary to successfully complete both the washout and PK sampling. If a participant experiences a bleeding episode after receiving the dose of BIVV001 but prior to completing the PK sampling, PK sampling will be stopped at the time of the bleed.

Washout and pk sampling requirements

Screening: all participants
	
Washout
 
 • First attempt: Washout of at least 48 hours before Screening inhibitor test to obtain interpretable test results^a. Repeat this washout if participant treats a bleed prior to 48 hours (follow second attempt). • Second attempt: Conduct same washout as first attempt. • If the second attempt at washout fails, additional attempts may be considered after consultation with the medical monitor^a.

Baseline PK sampling: PK subgroup
	

Day 1 Baseline PK sampling: 12 subjects <6 years of age
	
Washout
 
 • First attempt: Washout of at least 72 hours (3 days); repeat this washout if participant treats a bleed prior to 72 hours (follow second attempt)^a. • Additional attempt(s): Conduct same washout as first attempt^a. • If the second attempt at washout fails, additional attempts may be considered after consultation with the medical monitor. 
PK Sampling
 
 • First attempt: PK sampling period with collection of PK samples (Table 2) to 168 hours (Day 8) is required. If a participant treats a bleeding episode after receiving the dose of BIVV001 for PK evaluation but prior to completing the PK sampling period, PK sampling will be stopped at the time of the bleed and a second attempt (repeat) PK sampling period should be conducted. • Second attempt: Participants are required to undergo a 240 hour (10 Day) washout from the prior BIVV001 dose, which is then followed by the PK sampling period with collection of PK samples (Table 2) to 168 hours (Day 8). • If the second attempt at PK sampling period fails due to the participant treating a bleed prior to collection of the 168-hour (Day 8) sample, the participant will remain in the study but will no longer be included in the PK subgroup. The participant will be replaced in the PK subgroup and will continue with prophylactic BIVV001 dosing regimen.

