
Day 1 Baseline PK sampling: 12 subjects 6 to <12 years of age
	
Washout
 
 • First attempt: Washout of at least 96 hours (4 days); repeat this washout if participant treats a bleed prior to 96 hours (follow second attempt)^a. • Additional attempt(s): Conduct same washout as first attempt. If the second attempt at washout fails, additional attempts may be considered after consultation with the medical monitor^a. 
PK Sampling
 
 • First attempt: PK sampling period with collection of PK samples (Table 2) to 168 hours (Day 8) is required. If a participant treats a bleeding episode after receiving the dose of BIVV001 for PK evaluation but prior to completing the PK sampling period, PK sampling will be stopped at the time of the bleed and a second attempt PK sampling period should be conducted.

- Second attempt: Participants are required to undergo a 240 hour washout^a after previous dose, which is then followed by the PK sampling period with collection of PK samples (Table 2) to 168 hours (Day 8).
- If the second attempt at PK sampling period fails due to the participant treating a bleed prior to collection of the 168-hour (Day 8) sample, the participant will remain in the study but will no longer be included in the PK subgroup. The participant will be replaced in the PK subgroup and will continue with prophylactic BIVV001 dosing regimen.

Peak and trough sampling: All Participants except PK subgroup at Day 1

Washout

- First attempt: Washout of at least 72 hours (3 days) or 96 hours (4 days) for < 6 yr and 6 to <12 yr participants, respectively; repeat this washout if participant treats a bleed prior to 72 hours and 96 hours for <6 yr and 6 to <12 yr participants respectively (follow second attempt)^a.
- Additional attempts: Conduct same washout as first attempt.
- If the second attempt at washout fails, additional attempt may be considered after consultation with the medical monitor.

PK Sampling

- Collection of sample at trough (immediately pre-injection) and peak at 15 ±3 mins from start of injection. If the participant is being treated for an acute bleeding prior to collection of the peak and trough sample collection, no repeat sampling is needed and the patient will remain in the study and collect peak and trough at the next scheduled visit.

Peak and trough sampling: All Participants after Day 1

Washout

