4.4.2 ABR by type and location

ABR will be summarized descriptively by type and location for the following subsets of treated bleeds:

- Type of bleeding (spontaneous, traumatic, unknown)
- Location of bleeding (joint, muscle, internal, skin/mucosa)
- Location and type of bleeding (joint spontaneous, joint traumatic, muscle spontaneous, muscle traumatic, internal spontaneous, internal traumatic, skin/mucosa spontaneous, skin/mucosa traumatic)

The estimated mean ABR and the corresponding 95% CI will be provided, for each subset, using the same method as specified above. These tables will be presented by age cohort and overall for the FAS.

As a description of the raw data collected in this study, the unadjusted number of bleeding episodes per participant will be summarized using categorical (0, 1, 2, 3, 4, 5, and >5) and descriptive statistics overall and by bleed type (spontaneous, traumatic, unknown). The number

and percentage of participants experiencing a bleeding episode will be summarized categorically overall and by type of bleed (spontaneous, traumatic, unknown) as well as by bleed location (joint, muscle, internal, skin/mucosa, and unknown) for each bleed type; percentages will be based on the number of participants with an efficacy period. The total participant years followed during the efficacy period will be provided in order to put the un-annualized numbers in perspective.

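### Does a PK-sampled child who never completes a 168-hour profile drop out of the bleeding analyses?

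*SAP*

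**What the plan says.** SAP 4.1.1.2 has a general definition and three adjustments.

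- **General definition.** "The efficacy period is defined as the treatment period interrupted for PK periods", surgical/rehabilitation periods and large injection intervals. To be evaluable, "he/she must have at least 2 prophylactic dose of study drugs".
- **PK adjustment.** A child sampled after the first dose starts at the first prophylactic dose after a complete 168-hour period. If the first attempt is aborted, for example by a treated bleed, "then the efficacy period will begin following a subsequent fully executed PK sampling period".
- **Surgery.** "the efficacy period for the prophylactic regimen re-starts at the first prophylactic dose following the end of the surgical/rehabilitation period".
- **Large intervals.** Counting stops at the last injection before the gap, to "restart at the time of the next prophylaxis injection".

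SAP 4.1.1 adds that bleeding and consumption analyses leave out data collected during PK periods.

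Protocol 10.7.4 allows two PK attempts in each age cohort. If a treated bleed stops the second, "the participant will remain in the study but will no longer be included in the PK subgroup". It continues: "The participant will be replaced in the PK subgroup and will continue with prophylactic BIVV001 dosing regimen".

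**The concern.** The two documents do not quite meet. The PK adjustment ties the start of the efficacy period to a completed profile, and the protocol describes a child who will never have one. Surgery and large intervals each have a stated restart; the PK adjustment has none for this case.

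Taken word for word, the PK adjustment gives such a child no start date. His efficacy time would be zero, so he would contribute nothing to the ABR, the joint bleeding rate or annualized consumption. He would also leave the denominators in SAP 4.4.2, where "percentages will be based on the number of participants with an efficacy period". The reason would be that he bled twice in two short windows. That is exclusion on the outcome, and it would tend to lower the ABR. The older-cohort interim in SAP 4.9 would be most exposed, because it has 12 children and the protocol has the first 12 of each cohort PK-sampled.

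**Working it through.** **1. Is the child excluded? The text side by side.**

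- He has had at least one dose, so he is in the Full Analysis Set, on which efficacy is analysed (SAP 3 and 4.4).
- The one evaluability condition is two prophylactic doses. It says nothing about a completed profile, and a child continuing weekly prophylaxis meets it.
- The period is treatment time interrupted for PK periods. An interruption implies that counting resumes.
- SAP 4.1.1 removes data collected in PK periods, not the rest of a sampled child's year.
- The sentence about a fully executed period is worded as an explanation of the rule before it (count only once PK sampling is over), not as a separate exclusion.

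Read together, these keep the child. The start that respects all of them is the first prophylactic dose after the last attempt ends.

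**2. How likely is the case?** The documents give no treated-bleed rate for this product in children, so every rate here is an assumption. With rate λ per year and d = 7/365.25 = 0.01916 years, the chance of a bleed in one attempt is p = 1 − exp(−λd); two failures have chance p².

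Let λ vary between children as a gamma with mean m and shape k, and write L(t) = (1 + mt/k)^(−k). Then E[p²] = 1 − 2L(d) + L(2d). For m = 2, k = 0.5: L(d) = 0.96374, L(2d) = 0.93116, so E[p²] = 0.00368. Among 24 children, 1 − (1 − 0.00368)^24 = 8.5%.

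| Mean rate m | Shape k | At least 1 of 24 | Expected ABR shift on the literal reading, n = 65 |
|---|---|---|---|
| 1 | 2 | 1.3% | −0.02% |
| 1 | 0.25 | 3.7% | −0.43% |
| 2 | 2 | 4.8% | −0.07% |
| 2 | 0.5 | 8.5% | −0.50% |
| 2 | 0.25 | 12.2% | −1.4% |

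The shift compares m with (m − f·E[λp²])/(1 − f·E[p²]), where f = 24/65, E[λp²] = m − 2M(d) + M(2d) and M(t) = m(1 + mt/k)^(−k−1). For m = 2, k = 0.5: E[λp²] = 0.0343, giving (2 − 0.01265)/(1 − 0.00136) = 1.990. A cohort of 32 with 12 PK children gives nearly the same shifts. For the 12-child interim, all PK-sampled, the chance is 0.6% to 1.9% at m = 1 and 2.4% to 6.3% at m = 2; the expected shifts are −0.05% to −1.2% and −0.2% to −3.7%.

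**3. If it happened and he were dropped.** Take a group mean of 2.00 and a lost child with an assumed 10 bleeds a year:

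- n = 65: (130 − 10)/64 = 1.88; standard error √((2 + 4/0.5)/65) = 0.39
- n = 32: (64 − 10)/31 = 1.74; standard error √(10/32) = 0.56
- n = 12, 25 weeks (0.479 years): (24 − 10)/11 = 1.27; standard error √((2/0.479 + 8)/12) = 1.0

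The first two shifts are under half a standard error and the third under one. Ten a year is close to the expected rate of a double-failing child only near k = 0.5 (9.3). At k = 1 and k = 2 it is 5.8 and 3.9, and the n = 65 mean falls only to 1.94 and 1.97.

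**4. What separates the two workable starts?** Over 364 days, counting from the first dose gives 364 days. Counting from the first prophylactic dose after the second attempt, assumed at day 17 to 24 (10-day washout, 7-day attempt, up to a week to the next dose), gives 347 to 340. Suppose the child has 10 treated bleeds, two of them ending the attempts. His ABR is 10/364 × 365.25 = 10.0, or 8/347 × 365.25 = 8.4 to 8.6 with 340 days. The difference of 1.4 to 1.6, divided by 65, moves the overall mean by about 0.02.

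**The case for a change.** The best argument for a change is textual. The PK rule applies to anyone sampled after the first dose, not only to those still in the PK subgroup, so removal from the subgroup does not clearly release the child from it. The general definition defers to the adjustments that follow it, and they supply no start for him. Two programmers could therefore derive different results, and one derivation would depend on the outcome. One sentence would settle the matter at almost no cost.

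The missing start date stands: no other section supplies it. The bias argument does not carry the same weight, because it needs the least plausible reading, one that conflicts with the stated evaluability condition and with the use of the Full Analysis Set. The interim figure of 1.27 is striking, but it needs an event with a chance of 2.4% to 6.3% at a mean rate of 2, together with that reading.

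One further point is fair. Restarting after the last attempt still leaves out the two bleeds that ended the attempts. That follows from the plan's existing exclusion of PK periods, which applies to every PK child, and is not created by this gap.

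**Conclusion.** The gap is real but is missing detail that an analyst fills sensibly, so no change to the plan follows. The definition, the two-dose condition, the exclusion limited to PK-period data and the restart rules for surgery and large intervals all point to one derivation: resume at the next prophylactic dose after the last attempt. Dropping the child is a possible literal reading, not the stated plan.

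The size supports this. Under assumed gamma-distributed rates (mean 1 to 2 a year, shape 0.25 to 2), the case has about a 1.3% to 12% chance of arising. The expected shift is at most about 1.4% in the full sample even on the unfavourable reading, and about 0.02 in the mean ABR between the two workable starts in the example above. Higher rates would make the case more common: at a common rate of 5 a year, p = 0.0914 and p² = 0.00835, so 1 − (1 − 0.00835)^24 = 18%. The sensible derivation would be the same. All analyses are descriptive with no formal test, and the inhibitor endpoint and safety analyses do not depend on the efficacy period. No conclusion of the trial would change.

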4.1.1.3 Surgical/rehabilitation period

The broadest span of time for the surgical/rehabilitation period is from the first dose of BIVV001 given for the surgery (ie, the pre-surgery dose) up to 1 minute before the first regular prophylactic dose after the last day of postoperative care/rehabilitation.

Since not all participants will have these events, specific considerations for the start and end of the surgical/rehabilitation period are as follows:

Start of the surgical/rehabilitation period:

- If there is more than one pre-surgical dose, then the first one should be selected (a presurgical dose can be administered on the day or the day before surgery).
- If there is no pre-surgical dose but there was a prophylactic dose, or a dose given for "OTHER" reason prior to the surgery on the day of or the day before surgery, then the last of these doses should be selected.
- If there is no pre-surgical dose or no prophylactic dose on the day before surgery, then select the start date/time of the surgery. If the time was not recorded, then select the date and impute 00:01 for the time.

End of the surgical/rehabilitation period:

- If the participant resumed the prophylactic regimen following the surgical/rehabilitation period, then the end of the surgical/rehabilitation period is 1 minute before the first regular prophylactic dose after the latest date and time among the following (impute 23:59 if time is not available): 1) discharge from the hospital, 2) end of perioperative period follow-up phone call, and 3) end of a two-week period (one-week for minor surgeries) after the resumption of weekly prophylaxis treatment.
- If the participant did not resume the prophylactic regimen following the surgical/rehabilitation period (eg, the participant received no further prophylactic doses), then the end of the surgical/rehabilitation period is imputed as 23:59 on the last date among the following: 1) discharge from the hospital, 2) end of perioperative period follow-up phone call, and 3) end of a two-week period (one-week for minor surgeries) after the last surgical dose.

Statistical Analysis Plan BIVV001-EFC16295 23-Aug-2021 Version number: 1

• If the overall end of study is declared while the participant is still in the surgical/rehabilitation period, then select the date of the end-of-study visit and impute 23:59 for the time if a time is not provided.

Two exceptions are noted:

- If 2 (or more) major surgeries are performed without an intervening discharge from the hospital, then the first surgical/rehabilitation period will end 1 minute before the start of the next surgery and the second surgical/rehabilitation will end as described above. The same will also apply among overlapping minor surgeries.
- If minor surgery is performed during postoperative care or rehabilitation of a major surgery then the surgical/rehabilitation period for the minor surgery will start and end on the day of the minor surgery, at 00:01 and 23:59, respectively, if times are not otherwise provided or recorded as 00:00. The surgical/rehabilitation period for the major surgery will include the minor surgery (ie, the surgical/rehabilitation period for the major surgery does not stop and restart around the minor surgery) and will end as otherwise defined.

The surgical/rehabilitation period will be determined in the same manner for both major and minor surgeries.

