8.1.7 Assessment of response to surgery

The Investigators/Surgeons who complete the surgical procedures will assess the participant's response to surgery with BIVV001 treatment using a 4-point scale as described below. This includes observations during surgery and the 24-hour post-operative time period. This assessment will be performed 24 hours after the surgery.

Participants must have 6 EDs to BIVV001 and a negative inhibitor test within 4 weeks prior to surgery to be eligible for the surgery subgroup. Prior to surgery, the Investigator will plan the perioperative treatment regimen of FVIII replacement therapy generally required for the type of surgery in accordance with the dosing guidance in [Table 7](#). Recommendation for the appropriate dosing of BIVV001 in the surgical treatment period, including any rehabilitation time, will be discussed among the Investigator, Surgeon, and Sanofi BIVV001 Medical Monitor. Continuous infusions will not be allowed for this study.

Guidelines on surgical dosing are found in [Section 6.1.4](#). Pharmacokinetic samples taken during surgical procedures will be analyzed locally, but the site is requested to split the plasma and send an aliquot to the central laboratory for analysis.

Following a 24-hour post-operative study assessment, participants will follow the recommended postoperative treatment regimen as per Investigator's advice.

Data collected during the surgical/rehabilitation period for major and minor surgeries will be excluded from the analysis, including all bleeding episodes as well as the follow-up time during this period. The surgical/rehabilitation period will typically begin with the first dose of BIVV001 given for the surgery (ie, the pre-operative loading dose). The end of the surgical/rehabilitation period will occur with the latest of one of the following dates: 1) the date of discharge from the hospital; 2) the date of the perioperative period follow-up phone call; or 3) the end of a two-week period (one-week for minor surgeries) after the resumption of the participant's pre-surgery treatment regimen.

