4.4.14.2 Number of injections and dose to maintain hemostasis for major surgery

The number of injections, mean dose per injection (IU/kg), and total dose (IU/kg) required to maintain hemostasis during surgery will be summarized for all major surgeries for participants in the surgery subgroup. The number of injections per surgery will be summarized categorically (0, 1, 2, 3, 4, >4) and with descriptive statistics. Percentages for the categorical summary will be based on the number of major surgeries. The mean dose per injection and total dose required to maintain hemostasis will be summarized using descriptive statistics. The mean dose per injection will be determined as the average dose across all injections per major surgery (including the loading dose); the total dose will be determined as the sum across all injections (including the loading dose) per major surgery.

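### Read literally, the SAP's start bullets for the surgical/rehabilitation period skip the single pre-surgical dose and can start the period after the loading dose

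*SAP*

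**What the plan says.** SAP 4.1.1.3 begins with a general rule: "The broadest span of time for the surgical/rehabilitation period is from the first dose of BIVV001 given for the surgery (ie, the pre-surgery dose"). Protocol 8.1.7 agrees: "The surgical/rehabilitation period will typically begin with the first dose of BIVV001 given for the surgery (ie, the pre-operative loading dose"). Protocol 6.1.4 says the same for the surgery subgroup and gives the loading dose as 50 IU/kg.

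The SAP then lists three considerations for the start:

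- Bullet 1: "If there is more than one pre-surgical dose, then the first one should be selected".
- Bullet 2 opens "If there is no pre-surgical dose but there was a prophylactic dose" and extends to doses recorded as OTHER. It looks at the day of surgery and the day before, and takes the last such dose before the surgery.
- Bullet 3: "If there is no pre-surgical dose or no prophylactic dose on the day before surgery, then select the start date/time of the surgery". It adds: "If the time was not recorded, then select the date and impute 00:01 for the time".

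The section applies the same method to major and minor surgery. Under SAP 4.1.1.2, "the efficacy period continues up to 1 minute before the start of a surgical/rehabilitation period". SAP 4.4.9 sums all injections in the efficacy period and removes surgical doses only by period, not by the recorded reason for injection.

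**The concern.** The protocol describes one pre-operative loading dose as the usual start of surgical treatment, and no bullet names that case. Bullet 1 needs at least two pre-surgical doses and bullet 2 needs none. Bullet 3 is joined by *or*, so it is satisfied by the absence of prophylaxis the day before, even when a loading dose was given. It then places the start at the surgery, after that dose, against the section's own opening sentence.

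The boundary between the surgical and efficacy periods is at stake. A loading dose left on the wrong side counts as non-surgical consumption. For major surgery it is also missing from the overall surgical/rehabilitation-period total in SAP 4.4.14.3, although the day-of-surgery figure in the same section includes it. A treated bleed between the loading dose and incision would count toward the annualized bleeding rate.

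**Working it through.** The plan states no figure for this rule, so there is nothing to reproduce. The check has two parts: which bullets are met in each dosing pattern, and what one misplaced dose does to the summaries.

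**Which bullets are met.** The last column uses the wording proposed under the fix.

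| Pre-surgical doses | Prophylactic dose the day before | Prophylactic dose on the day, before surgery | Bullets met as written | Result | Bullet met after rewording |
|---|---|---|---|---|---|
| 0 | no | no | 3 | start of surgery, as intended | 3 |
| 0 | no | yes | 2 and 3 | conflict | 2 |
| 0 | yes | either | 2 and 3 | conflict | 2 |
| 1 | no | either | 3 | start of surgery, after the loading dose | 1 |
| 1 | yes | either | none | only the opening sentence applies | 1 |
| 2 or more | no | either | 1 and 3 | conflict | 1 |
| 2 or more | yes | either | 1 | first pre-surgical dose, as intended | 1 |

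Replacing *or* with *and* in bullet 3 is not enough. Bullets 2 and 3 would still both be met when there is no pre-surgical dose and no prophylaxis the day before, but a prophylactic dose on the day of surgery. The same holds for a qualifying OTHER dose, which bullet 3 does not mention.

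**Effect on annualized consumption.** SAP 4.4.9 divides total IU/kg in the efficacy period by days in that period and multiplies by 365.25. Assume weekly 50 IU/kg throughout and one misplaced 50 IU/kg loading dose.

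- Base rate: 50/7 × 365.25 = 2,608.9 IU/kg/year.
- 364 efficacy days: 50/364 × 365.25 = 50.2, giving 2,659.1 (+1.9%).
- 340 efficacy days: 50/340 × 365.25 = 53.7, giving 2,662.6 (+2.1%).
- About 26 weeks (182.625 days): 50/182.625 × 365.25 = 100.0, giving 2,708.9 (+3.8%).
- Mean of 65 participants, 340 efficacy days: 53.7/65 = 0.83 IU/kg/year per affected surgery, and 0.83/2,608.9 = 0.03%.

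**Effect on the overall-period total (major surgery only).** The documents give no expected total, so this range is illustrative.

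- A loading dose plus two to three further doses of 30 or 50 IU/kg (Protocol 6.1.4) runs from 50 + 2 × 30 = 110 to 50 + 3 × 50 = 200 IU/kg.
- For a participant who resumes prophylaxis, the period lasts at least two weeks beyond resumption, so it also contains about two to three weekly 50 IU/kg doses, or 100 to 150 IU/kg.
- The full total is then 210 to 350 IU/kg, and the missing dose is 50/350 = 14% to 50/210 = 24% of it.

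**The case against.** The strongest reply is that the opening sentence already settles the single-dose case. The bullets are introduced as considerations for participants who lack some of the events, and a participant with one loading dose lacks nothing at the start. A literal *or* would also mean that bullet 2 never operates without bullet 3 contradicting it, which suggests that the author meant *neither*. The adverse-event rule in SAP 4.7.2 assumes that the period can begin with a pre-surgical dose given the day before. All of this stands as evidence of intent. It does not repair the operative text, which contradicts itself and the opening sentence and leaves a programmer to choose.

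Three stronger readings are tempting, and the documents do not support them.

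- **That the loading dose will be misallocated in the ordinary case.** That needs the bullets programmed as written against the stated intent, and a dose that precedes the selected start. If the surgery time is missing, the 00:01 imputation keeps a same-day dose inside the period; a dose from the day before would still fall outside.
- **That about six in seven surgeries are exposed under weekly dosing.** This assumes that timing is unrelated to the dosing day. Protocol 4.3 allows minor procedures to be planned around a standing prophylactic dose, in which case there is no separate loading dose.
- **That surgical dose reporting is generally compromised, with 25–45% of the total lost.** That share comes from 50/200 and 50/110, which omit the resumed weekly doses. SAP 4.4.14.2 defines its total independently of the period start: "the total dose will be determined as the sum across all injections (including the loading dose) per major surgery". Its number of injections and mean dose are also unaffected, as is day-of-surgery consumption in 4.4.14.3. Minor surgeries have no overall-period total to distort.

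**Conclusion.** The rule is wrong as written, and the effect is small. The start bullets do not implement the section's own definition for a single pre-surgical dose, and bullet 3 conflicts with both of the others. Under literal programming, one affected participant's total annualized consumption rises by about 2% to 4%, depending on the length of the efficacy period, and the cohort mean moves negligibly. The only display with a visible relative change is the overall-period total for major surgery. Its 14–24% share rests on the assumed number of further and resumed doses.

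The bleed-misassignment window runs only from loading dose to incision and is short. The primary inhibitor endpoint is unaffected, because SAP 4.3.1 keeps samples from surgical periods. All analyses are descriptive, so no test result depends on this.

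**What to change.** Reword two bullets in SAP 4.1.1.3 before database lock:

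- Bullet 1: *If there is one or more pre-surgical dose, select the first.*
- Bullet 2: unchanged.
- Bullet 3: *If there is neither a pre-surgical dose nor a prophylactic or OTHER dose prior to the surgery on the day of or the day before surgery, select the start date/time of the surgery.*

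Exactly one bullet then applies to every pattern in the table, and the result matches the opening sentence and Protocol 6.1.4 and 8.1.7. The cost is SAP wording and the matching line of the programming specification. Nothing changes in trial conduct or data collection.
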